Project Title: Probing the Synergistic Effect of Pre-biotics & Iron Fortificants in Anemic Subjects	
Principal Investigator: [name]	
NCT No.: NCT03894449	
Date: January 11, 2019	
IRC Ref No. :	Organization: UVAS, Lahore
Address: UVAS, [name]	[contact]
Other Investigators: [name]	Organization: UVAS, Lahore
Address: UVAS, [name]	[contact]

MATERIALS AND METHODS

The study will consist of determining the synergistic effect of pre-biotics and iron fortificants in anemic human subjects.

Study Design

A double blind, randomized controlled trial will be used for the purpose of this study.

Study Site

The study will be conducted in Islamabad and/or Lahore, depending on the availability of the required sample size with the desired profiles.

Study Duration

The trial will last for 3 months.

Study Population

The study population will comprise of university going iron deficient female adults (age 18-25 years).

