3.3.6 Treatment Plan

For this phase of the study, 4 best treatment combinations of pre-biotics and iron fortificants will be chosen based on the results of animal trials while one group will be taken as control (Table 1).

Table 1: Treatment Plan for Anemic Women

GROUP	DIET PLAN
D ₀	Control Group (Placebo)
D ₁	Best Treatment Combination 1
D ₂	Best Treatment Combination 2
D ₃	Best Treatment Combination 3
D ₄	Best Treatment Combination 4

Study participants will be randomly chosen to receive either the best treatment combination 1, 2, 3, 4 or the placebo for 12 weeks on daily basis.

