3.3.7.6 Statistical Analysis

In order to determine the level of significance, the statistical analysis of the obtained data will be done for the purpose of which, SPSS version 23.0 will be used. CRD will be used during the experiment and differences will be considered significant at P - value < 0.05 (Steel and Torrie 1980).

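### The stated aim is synergy, but with only placebo and combination arms the trial cannot separate synergy from iron alone, prebiotic alone or simple addition

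*Combined protocol and SAP*

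**What the plan says.** The title announces synergy, "Probing the Synergistic Effect of Pre-biotics & Iron Fortificants in Anemic Subjects", and the first sentence of Materials and Methods makes it the aim in people: "The study will consist of determining the synergistic effect of pre-biotics and iron fortificants in anemic human subjects". No other aim is stated.

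Section 3.3.6 describes the active arms: "4 best treatment combinations of pre-biotics and iron fortificants will be chosen based on the results of animal trials". Allocation is among these and placebo only: "Study participants will be randomly chosen to receive either the best treatment combination 1, 2, 3, 4 or the placebo". Table 1 lists D0 as placebo and D1 to D4 as the four combinations, without their composition.

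Section 3.3.4.1.2 excludes women already taking iron or prebiotic supplements, so background use does not supply a single-component group. Section 3.3.5.2 sets 15 women per group and 75 in total.

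On analysis, section 3.3.7.6 names the software and adds: "CRD will be used during the experiment and differences will be considered significant at P - value < 0.05". I take CRD to mean completely randomised design. The section gives no definition of synergy, interaction contrast or dose-response model.

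**The concern.** Synergy means that the two components together do more than the sum of what each does alone. Estimating it needs four quantities: the response to the combination, to iron alone, to prebiotic alone, and to neither. The plan observes the first and the last.

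Iron could by itself improve iron markers in iron-deficient women. A significant combination-versus-placebo result is what one would see if the prebiotic did nothing. Under the present title and aim it would invite a conclusion of synergy that the data cannot support. Nor could any result from these arms refute synergy. This is a failure of identifiability, not of precision: more women in the same five arms would not cure it.

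**Working it through.** **Inputs.** Five arms of 15 (section 3.3.5.2): 5 × 15 = 75, which reproduces the stated total. Error degrees of freedom are 75 − 5 = 70. The significance level is 0.05 (section 3.3.7.6), taken as two-sided. The plan gives no effect size, SD or power, so every effect size below is an assumption, in SD units.

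**Step 1: what the arms identify.** Let *I* be the effect of iron alone, *P* of prebiotic alone and *S* the interaction (synergy if positive). If D1 to D4 each contain both components and D0 neither:

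- D0 mean = μ
- D1 to D4 mean = μ + *I* + *P* + *S*

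Coding each component as present or absent, the arms-by-parameters matrix has rank 2 for four parameters (μ, *I*, *P*, *S*). Adding the row for *I* + *P* + *S* leaves the rank at 2, so that sum is estimable. Adding the row for *I*, for *P* + *S* (what the prebiotic adds to iron) or for *S* raises it to 3, so none of these is estimable.

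**Step 2: different truths, same data.**

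| Truth | *I* | *P* | *S* | Combination − placebo |
|---|---|---|---|---|
| Iron only | 1 | 0 | 0 | 1.0 |
| Prebiotic only | 0 | 1 | 0 | 1.0 |
| Addition | 0.5 | 0.5 | 0 | 1.0 |
| Synergy | 0.25 | 0.25 | 0.5 | 1.0 |
| Antagonism | 0.8 | 0.8 | −0.6 | 1.0 |

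**Step 3: could the unstated compositions rescue it?**

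- *Two fortificant types × two prebiotic types, plus placebo.* The rank is 5. It rises to 6 for a single interaction or for the average interaction, so synergy is still not estimable. One prebiotic versus the other with the same fortificant is estimable (rank stays 5), but that compares formulations.
- *Two amounts × two amounts, plus placebo.* With linear effects and a product term the rank is 4 of 4, so an interaction can be fitted, but only under that assumed dose-response model. The plan states neither the crossing nor the model.

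**Step 4: how readily the trial could be significant with no synergy.** Suppose iron does everything, so all four combinations are shifted by *d*, with *P* = *S* = 0. The first two rows are simulated (400,000 trials, pooled variance, 70 df). The third is the noncentral F(4, 70) with λ = 15 × 0.8 × *d*².

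| Rule | 0.3 | 0.5 | 0.8 | 1.0 | 1.2 SD |
|---|---|---|---|---|---|
| Any of four unadjusted t tests vs D0 | 31% | 55% | 86% | 96% | 99% |
| Any of four Dunnett tests (critical value 2.504) | 15% | 33% | 68% | 86% | 96% |
| Overall F test | 11% | 23% | 55% | 77% | 92% |

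The plan does not say which rule applies.

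**Step 5: what adding component-alone arms would buy.** An iron-alone arm by itself raises the rank in step 1 to 3: *P* + *S* becomes estimable, *S* does not. With both component-alone arms the rank is 4 and synergy is estimable.

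- Synergy contrast (combination − iron − prebiotic + placebo): SE = √(4/15) = 0.516 SD. Power with 70 df is 16%, 33%, 48% and 82% for 0.5, 0.8, 1.0 and 1.5 SD; 80% power needs about 1.47 SD.
- Combination − iron alone: SE = √(2/15) = 0.365 SD. Power is 27%, 58% and 77% for 0.5, 0.8 and 1.0 SD.
- 80% power for a 0.8 SD interaction: n = 4 × ((1.960 + 0.842)/0.8)² ≈ 49.1, so 50 per arm, or 4 × 50 = 200 women in a 2×2.

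**The case against.** **Compositions are not given.** D1 to D4 are still to be chosen, so reading each as containing both components is an inference. It is the natural one, since section 3.3.6 describes combinations of the two. Step 3 covers the alternatives, and none gives synergy without a model that the plan lacks. The qualification stands: synergy is not identifiable from the design as described.

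**This is one phase of a larger project.** The animal work may have included single-component groups. The plan uses that work only to choose combinations, however, and sets its aim in human subjects. Animal data do not answer that aim.

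**The word may loosely mean combined.** If so, the trial does what was intended and the defect is terminology. The plan does not define the word, readers will take its ordinary meaning, and the correction costs almost nothing.

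**The step 4 figures would be the same if synergy were real.** This stands. They show how easily a significant result arises without synergy; they do not measure the defect, which rests on steps 1 and 2.

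**The step 5 power ignores baseline adjustment.** This also stands. If a baseline value were available and correlated 0.5 to 0.7 with outcome (assumed), interaction power at 15 per arm would be about 42% to 57% at 0.8 SD and 60% to 76% at 1.0 SD. The step 5 costs are therefore at the upper end.

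**Conclusion.** The concern holds, and correction is needed before the trial starts. As described, the trial provides valid randomised comparisons of each combination with placebo but cannot determine synergy, its only stated aim, nor what the prebiotic adds to iron. That conclusion rests on each of D1 to D4 containing both components and D0 neither. It needs no assumption about effect size, and no sample size changes it. The one exception would be crossed amounts analysed under an assumed dose-response model, which the plan does not describe.

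**What to change.** **Required, wording only.** Restate the title and the opening aim as the effect of combined prebiotic and iron fortificant versus placebo in anemic women. Add a sentence such as: *The design has no iron-alone or prebiotic-alone arm; neither synergy nor an added benefit of the prebiotic over iron will be claimed.* Arms, sample size and procedures stay as they are.

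**Optional, only if the sponsor wants to keep the synergy aim.** Before randomisation, amend the plan to replace two of the combination arms with the iron-alone and prebiotic-alone counterparts of a retained combination. Pre-specify two contrasts: combination − iron alone (added value of the prebiotic) and combination − iron − prebiotic + placebo (synergy). The price is that two combinations are compared instead of four. At 15 per arm, synergy becomes estimable but is unlikely to be detected unless very large. About 200 women in a 2×2 would be needed for 80% power at 0.8 SD without baseline adjustment.

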3.3.5. Sampling

3.3.5.1 Sampling Technique

The technique of convenience sampling will be used for the current study.

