3.3.5.2 Sample Size

Each group will consist of 15 study subjects for the purpose of convenience and the total sample size will be 75.

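### If both cities are used, a completely randomised design gives up precision by city that a city term and stratified allocation would keep at almost no cost

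*Combined protocol and SAP*

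**What the plan says.** The Study Design paragraph states: "A double blind, randomized controlled trial will be used for the purpose of this study". On location, the Study Site paragraph says: "The study will be conducted in Islamabad and/or Lahore, depending on the availability of the required sample size with the desired profiles". A two-city trial is therefore a planned possibility, with the mix left to recruitment. Section 3.3.5.1 adds: "The technique of convenience sampling will be used for the current study", so nothing fixes how many women come from each city.

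Section 3.3.5.2 sets the size: "Each group will consist of 15 study subjects for the purpose of convenience and the total sample size will be 75". Section 3.3.6 describes allocation only as "Study participants will be randomly chosen to receive either the best treatment combination 1, 2, 3, 4 or the placebo". Section 3.3.7.6 gives the layout and threshold: "CRD will be used during the experiment and differences will be considered significant at P - value < 0.05". I read CRD as completely randomised design, which fits a statistical section of a randomised trial. No section mentions strata, blocks, a site or city factor, or any covariate.

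**The concern.** A completely randomised design has no blocks. If women come from two cities, the number from each city in an arm is left to chance, and an analysis by arm alone puts any difference between city means into the error term. With 15 women per arm and no power calculation, there is no known margin to absorb avoidable variance.

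Allocation is random, so this is not systematic confounding: the unadjusted contrast is unbiased and its type I error over all allocations is preserved. What is at stake is power and the width of the confidence intervals. The extra variance of the unadjusted contrast is the chance city imbalance averaged over allocations, so imbalance and lost precision are one harm and should not be counted twice.

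**Working it through.** **Inputs from the documents.** Five arms of 15; 5 × 15 = 75, which reproduces the stated total. Significance at 0.05, taken as two-sided because the plan does not say. There is no power calculation to reproduce.

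**Assumed inputs.** The documents give no effect size, SD, city split or city difference. I take a within-city SD of 1, no dropout, m women from the smaller city (m = 15, 25 or 37 of 75), and a difference in city means of g = 0.25, 0.5 or 1.0 SD. The reference treatment effect is 1.04 SD, the difference detectable with about 80% power at 15 per arm when the cities do not differ.

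**Step 1: imbalance.** Let k = m(75 − m)/(75 × 74). The difference between two arms in their number of women from one city has variance 2 × 15 × k, so its root-mean-square (RMS) is √(30k). The probabilities come from 200,000 simulated allocations.

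| City split | k | RMS difference (women of 15) | A given contrast off by ≥5 | At least one of four off by ≥5 |
|---|---|---|---|---|
| 15/60 | 0.162 | 2.2 | 4% | 12% |
| 25/50 | 0.225 | 2.6 | 8% | 24% |
| 37/38 | 0.253 | 2.8 | 10% | 29% |

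**Step 2: variance.** Without a city term, the variance of a pairwise contrast is (2/15) × (1 + k g²). The equivalent arm size is 15 × (1 + k g²), the number per arm that an unadjusted analysis would need to match 15 per arm with the city effect removed.

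- 37/38: the factor is 1.016, 1.063 or 1.253 at g = 0.25, 0.5 or 1.0. Equivalent arm sizes are 15.2, 16.0 and 18.8.
- 15/60: the factor is 1.010, 1.041 or 1.162.

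To confirm that steps 1 and 2 describe the same harm, take 37/38 and g = 1.0. The mean squared imbalance in proportions is (2.757/15)² = 0.0338, and the extra variance is 0.2533 × 2/15 = 0.0338.

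**Step 3: power.** With no city effect the noncentrality is 1.04/√(2/15) = 2.848. On 70 error df (75 − 5) this gives 80.2%. With a city effect and no city term, the noncentrality is divided by √(1 + k g²).

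| City split | g = 0.25 | g = 0.5 | g = 1.0 |
|---|---|---|---|
| 37/38 | 79.6% | 77.8% | 70.9% |
| 15/60 | 79.8% | 78.6% | 74.1% |
| 10/65 | 79.9% | 79.1% | 75.7% |

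**Step 4: after the change.** With city balanced across arms and in the model, the standard error returns to √(2/15) = 0.365 SD. The error df fall from 70 to 69, and power at 1.04 SD stays at 80.2%.

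**Step 5: simulation at 37/38, g = 1.0 (20,000 trials).** Power was 70.9% for complete randomisation without a city term, 79.5% for complete randomisation with the term, and 79.8% for blocks within city with the term. Type I error of the unadjusted contrast under complete randomisation was 5.0% at g = 0.5 and 4.9% at g = 1.0. A separate simulation (10,000 trials) of stratified allocation without the term gave a type I error of 2.8% at g = 1.0, so that test is conservative.

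**The case against.** The loss depends on things the documents do not state: whether both cities are used, the split, and the city difference. At the worst split it is 0.6 power points at 0.25 SD and 2.4 points at 0.5 SD. It reaches about 9 points only when the cities differ by about as much as the reference treatment effect. The entry criteria select young, unmarried university students with no chronic disease and no current iron or prebiotic supplements, which should narrow city differences. A second city used only to top up recruitment would give a lopsided split and a smaller loss. Adjustment for a baseline value would absorb part of a persistent gap: with an assumed correlation of 0.6, a 1.0 SD gap acts like (1 − 0.6)/√(1 − 0.6²) = 0.5 SD, cutting the inflation at 37/38 from 25% to about 6%. Finally, the city term does nearly all the work; stratifying adds less than one power point.

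All of this limits the size of the benefit, and the last point sets the priority within the fix. None of it removes the point. The plan expressly allows two cities, names a design without blocks, and specifies neither a city term nor baseline adjustment. Stratification cannot be added once women are randomised, and a city term chosen after seeing the data is open to question in a way that a prespecified one is not.

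**Conclusion.** The concern holds, conditional on both cities being used. Complete randomisation with no city term then leaves avoidable variance in every comparison with placebo. Across city differences of 0.25 to 1.0 SD, the loss is 0.6 to 9.3 power points at 37/38 (80.2 − 79.6 to 80.2 − 70.9) and 0.4 to 6.1 points at 15/60 (80.2 − 79.8 to 80.2 − 74.1). It is zero with one city or no city difference. These figures assume a 1.04 SD effect, equal within-city SDs, two-sided testing at 0.05, no dropout and no baseline adjustment. Validity is not threatened. The change should be made because it is nearly free and the sample has little precision to spare. Confidence in its practical importance is medium, since the split and the city difference are unknown.

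**What to change.** State in the protocol that, if women are enrolled in both cities:

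1. City is a prespecified factor in the analysis model. This recovers nearly all the lost power.
2. Allocation uses permuted blocks in multiples of 5, from a separate list for each city, in place of the completely randomised design. With blocks of exactly 5, two arms differ by at most 1 woman within a city; larger blocks loosen that bound.

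The two parts belong together, because stratifying without the term makes the test conservative when the cities differ.

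The cost is a second randomisation list and one error degree of freedom (69 instead of 70). If the city totals are not multiples of 5, arm sizes may be 14 to 16 instead of exactly 15: at 37/38, for example, each city ends on an incomplete block. No extra women or procedures are needed. If only one city is used, no change is required on this point.

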3.3.4.1 Inclusion and Exclusion Criteria

3.3.4.1.1 Inclusion Criteria

All willing anemic female adults without any chronic diseases such as diabetes or hypertension will be included in the study.

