3.3.4.1.2 Exclusion Criteria

Married females or those with chronic diseases or those already taking iron and/or prebiotic supplements will be excluded from the study.

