3.3.7 Efficacy Trials

Up to three months, blood samples will be collected from overnight fasted women on monthly basis.

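### Entry has no lower haemoglobin limit and no action follows from the monthly haemoglobin, so a severely anaemic woman, if enrolled, has a 1 in 5 chance of 12 weeks of placebo with no Hb-based safeguard in the supplied text

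*Combined protocol and SAP*

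**What the plan says.** **Who enters.** The inclusion rule (3.3.4.1.1) is "All willing anemic female adults without any chronic diseases such as diabetes or hypertension will be included in the study". Anaemia is not defined by an Hb value, and no floor is set. The Study Population paragraph adds that the women are iron-deficient university students aged 18 to 25. The Study Site paragraph says that the city will be chosen "depending on the availability of the required sample size with the desired profiles", without saying what those profiles are. Recruitment is by convenience sampling (3.3.5.1).

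**Who is kept out.** Section 3.3.4.1.2 excludes married women and women with chronic disease, and adds that "those already taking iron and/or prebiotic supplements will be excluded from the study". Severe anaemia is not on the list.

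**What they receive.** Section 3.3.5.2 states: "Each group will consist of 15 study subjects for the purpose of convenience and the total sample size will be 75". In 3.3.6, one of the five groups (D0) is placebo. Women are randomised to one of four active combinations "or the placebo for 12 weeks on daily basis". The iron content of D1 to D4 is not stated, because the combinations are to be chosen from animal results.

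**What is monitored.** Under 3.3.7, "blood samples will be collected from overnight fasted women on monthly basis", and 3.3.7.1 includes Hb for all groups. Liver and renal tests follow in 3.3.7.3 and 3.3.7.4. Section 3.3.7.7 provides for committee approval, written consent and confidentiality. None of these sections links an Hb value to an entry, referral, treatment or unblinding decision.

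**The concern.** Three features combine. The entry rule has no floor. Entrants are by design not taking iron supplements when they join. The trial is double blind, so a low Hb prompts a response only if a rule requires one, and no such rule is written.

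Followed literally, the plan lets a woman for whom a 12-week delay in treatment is not acceptable be randomised to placebo. Her month-1 and month-2 Hb would be recorded as efficacy data, with nobody required to act on them. What is at stake is participant safety, not the validity of the comparison. It is also a gap that the trial's own measurements could close.

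**Working it through.** **Inputs from the documents.** Five groups of 15, total 75 (3.3.5.2). One group is placebo, with 12 weeks of daily dosing (3.3.6). Sampling is monthly for up to three months (3.3.7). Significance is at P < 0.05 (3.3.7.6). No allocation ratio is written; equal allocation is inferred from the equal group sizes.

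**The plan's own figure.** 5 × 15 = 75, which matches the stated total.

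**Chance of placebo for one entrant.** 15/75 = 0.20.

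**Chance that at least one of k severely anaemic entrants is in D0.** With group sizes fixed, this is 1 − C(75 − k, 15)/C(75, 15). The value of k is an assumption, since the documents do not give it.

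| k | At least one in D0 |
|---|---|
| 1 | 20% |
| 2 | 36% |
| 3 | 49% |
| 5 | 68% |

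**What acting on the monthly Hb could save.** Taking a month as 4 weeks, action at month 1 spares 12 − 4 = 8 weeks of placebo, and action at month 2 spares 12 − 8 = 4 weeks.

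**What treating placebo women would cost the comparison.** If k of the 15 women in D0 are treated and each gains g times the active effect, the D0 contrast shrinks by k × g/15. The values of k and g are assumed.

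| Treated in D0 | g = 0.5 | g = 1 | g = 2 |
|---|---|---|---|
| 1 | 3% | 7% | 13% |
| 2 | 7% | 13% | 27% |

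The plan states no power, so I took a contrast that has 80% power before any loss. The assumed test is an unadjusted pairwise t test, two-sided at 0.05, with 15 per group and a pooled variance on 75 − 5 = 70 degrees of freedom. Power of 80% then needs a standardised difference of d = 1.037, a noncentrality of 1.037 × √(15/2) = 2.84. Multiplying d by (1 − loss) gives:

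| Loss | d after loss | Power |
|---|---|---|
| 6.7% | 0.968 | 74% |
| 13.3% | 0.899 | 68% |
| 26.7% | 0.761 | 54% |

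These are scenarios, not bounds. Extra treatment of women in D1 to D4 would push the contrast the other way.

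**The case against.** **The harm may never arise.** The population is young, unmarried, at university and free of chronic disease, and convenience sampling lets the investigator shape the case mix. A reader might infer that severely anaemic women will be enrolled and harmed. The documents do not support that: they give no baseline Hb distribution and no count. Any overall probability would only restate an assumed share p through 1 − (1 − p)^15, with recruits treated as independent: 1.5% at p = 0.1%, 79% at p = 10%. The 1 in 5 is likewise every entrant's chance of placebo and does not measure harm. All of this stands. It limits the size of the claim but does not supply a safeguard.

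**A safeguard may exist elsewhere.** The text begins at the methods, refers to itself as one phase of a study, and comes without its consent pages. The committee could also impose a limit. A reader might infer that participants have no protection at all; that goes too far, since approval, consent, monthly Hb and organ-function tests are all planned. The claim is only that the supplied text contains no Hb-based rule.

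**Existing wording might already narrow entry.** The desired profiles are undefined and appear as a reason for choosing a site. The chronic-disease criterion names diabetes and hypertension; it is not an Hb limit. Neither excludes severe iron-deficiency anaemia.

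**The focus on placebo is itself an assumption.** It is tempting to treat D1 to D4 as safe because they contain iron fortificants. With no dose stated, that cannot be assumed. This objection stands, and it is why the monthly rule should cover every arm.

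**Conclusion.** The point holds in conditional form. As supplied, the plan states an entry rule with no Hb floor, does not exclude severe anaemia, and attaches no action to the monthly Hb. A severely anaemic woman, if enrolled, would have a 20% chance of 12 weeks of placebo without any Hb-based safeguard in the supplied text.

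The omission can be read directly from the document. The 20% rests only on the equal allocation that groups of 15 imply. How many women would be exposed is unknown, as is whether the active combinations would be adequate for them. Confidence in the practical importance is therefore medium. The rule should still be written before enrolment, because the possible harm falls on participants and a safeguard costs little when it is not used.

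**What to change.** **Section 3.3.4.1.1.** Exclude women below a lower Hb limit, set with the Institutional Review Committee before enrolment, and refer them for care. Apply it to the Hb that establishes anaemia at entry. The value is for the investigator and the committee to choose; the documents offer no basis for one here.

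**Section 3.3.7.1.** State that any monthly Hb below a pre-set limit, in any arm, leads to prompt referral or treatment, and that the woman remains in her randomised group for analysis.

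**Cost.** Two short additions and a committee decision. The total of 75 is unchanged and monitoring needs no extra blood draw, but up to 75 × 3 = 225 monthly Hb results must be read promptly. An entry Hb must be available before randomisation; the plan describes no screening sample, so if none is taken already, that is an added step. A few women may be turned away. Treating placebo women would dilute the contrast as calculated above, down to about 54% power in the most severe scenario listed. The entry limit should keep such treatment rare.
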